9.3.2 Pharmacokinetic Statistical Methodology

Pharmacokinetic parameter estimates will be evaluated to determine the impact of changes in gastric motility that may accompany acute migraine attacks on the PK of lasmiditan and its metabolites. All plasma concentration data and derived PK parameters will be summarized by period (i.e., migraine status; lasmiditan administered during a migraine versus lasmiditan administered during the inter-ictal period).

Log-transformed C_{max} , AUC(0-tlast), and AUC(0-∞) parameters will be evaluated in a linear mixed-effects model with a fixed effect for period (ie, migraine status; lasmiditan administered during a migraine versus lasmiditan administered during the inter-ictal period) and a random effect for patient. The treatment period differences will be back transformed to present the ratios of geometric means and the corresponding 90% confidence interval.

An example of the SAS code that will be used is as follows:

```
proc mixed data=xxxx;
class period subjid;
model l_pk = period / alpha=0.1;
random subjid;
lsmeans period / pdiff;
run;
```

where l_pk is the log-transformed (base e) PK parameter.

The t_{max} will be analyzed using a Wilcoxon signed rank test. Estimates of the median difference based on the observed medians, 90% confidence intervals, and the p-value from the Wilcoxon test will be calculated.

Additional analysis may be performed if warranted upon review of the data. Insert stats methodology here.

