#### 10.3.2.2. Pharmacokinetic Statistical Inference

Pharmacokinetic parameter estimates will be evaluated to determine the impact of changes in gastric motility that may accompany acute migraine attacks on the PK of lasmiditan and its metabolites. Log-transformed  $C_{max}$ ,  $AUC(0\text{-}t_{last})$ , and  $AUC(0\text{-}\infty)$  parameters will be evaluated in a linear mixed-effects model with a fixed effect for period (ie, migraine status; lasmiditan administered during a migraine versus lasmiditan administered during the inter-ictal period) and a random effect for patient. The treatment differences will be back transformed to present the ratios of geometric means and the corresponding 90% confidence interval.

The tmax will be analyzed using a Wilcoxon signed rank test. Estimates of the median difference based on the observed medians, 90% confidence intervals, and the p-value from the Wilcoxon test will be calculated.

Additional analysis may be performed if warranted upon review of the data.

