7. SAMPLE SIZE JUSTIFICATION

Approximately 20 patients may be enrolled to ensure 12 patients with adequate PK data complete the study. Patients who do not complete both periods of the study may be replaced.

For area under the concentration versus time curve (AUC) or maximum observed drug concentration (C_{max}), assuming inter-patient CV% of 40% (based on previous studies) and a sample size of 12, the 90% confidence interval (CI) around the geometric mean of the within-patient ratios (migraine/inter-ictal) will have a half-width of 20.1% with 90% coverage probability.

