11. CHANGES FROM THE PROTOCOL SPECIFIED STATISTICAL ANALYSES

There were no changes from the protocol specified statistical analyses.

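### Does the example SAS code in SAP 9.3.2 fail to deliver the 90% confidence interval that the text promises?

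*SAP*

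**What the plan says.** The text of SAP 9.3.2 puts log-transformed Cmax, AUC(0-tlast) and AUC(0-∞) into a linear mixed model with a fixed effect for period (that is, migraine status) and a random effect for patient. The period differences are to be "back transformed to present the ratios of geometric means and the corresponding 90% confidence interval". Protocol 10.3.2.2 makes the same commitment: "The treatment differences will be back transformed to present the ratios of geometric means and the corresponding 90% confidence interval". The protocol synopsis repeats it.

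The code that follows is introduced with "An example of the SAS code that will be used is as follows" and uses a placeholder dataset name. The statements that matter are:

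- "model l_pk = period / alpha=0.1"
- "random subjid"
- "lsmeans period / pdiff"

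No other statement asks for limits, and none exponentiates anything. SAP 3 leaves the layout of the outputs to a separate TFL shell document, which is not among the public documents. SAP 11 declares: "There were no changes from the protocol specified statistical analyses".

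**The concern.** The ratio with its 90% interval is the main result for Cmax and the AUCs; the plan gives no test or no-effect bounds for them. The code is the only code given for that analysis, yet it does not ask for the interval. `ALPHA=` on MODEL governs limits on the fixed-effect coefficients only, and those are not requested. It does not carry over to LSMEANS, where `PDIFF` alone gives the difference and a p-value.

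The code serves 3 parameters for each of 6 analytes (lasmiditan and 5 metabolites), so 18 intervals depend on it. The practical worry is a silent error. A programmer who sees no limits in the output might add `CL` to LSMEANS and assume that the 0.1 already in the code applies. The LSMEANS default of 0.05 would apply instead, and 95% limits could go out under a 90% label.

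**Working it through.** **1. Is the intended level in doubt?** SAP 7 gives a precision figure that can be checked, "assuming inter-patient CV% of 40% (based on previous studies) and a sample size of 12", with a stated half-width of 20.1%.

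- SD on the log scale: √ln(1 + 0.40²) = 0.3853.
- Standard error with 12 patients: 0.3853/√12 = 0.1112.
- 90% level, normal quantile: exp(1.645 × 0.1112) − 1 = exp(0.1829) − 1 = 20.07%, which rounds to the stated 20.1%.
- 95% level, normal quantile: exp(1.960 × 0.1112) − 1 = 24.4%, which does not match.

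The sample size was therefore worked at 90%, as the text of both documents says, and an alpha of 0.1 is the same level. This reproduction treats the 40% CV as the variability of the within-patient log-ratio. Whether that suits an inter-patient CV is a separate matter.

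**2. What does the printed code give?**

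| Needed for the 90% interval | In the printed output? |
|---|---|
| Model with period fixed, patient random | Yes |
| Period 1 minus Period 2 difference, log scale | Yes, from LSMEANS with `PDIFF` |
| Its standard error and degrees of freedom | Yes, same table |
| Log-scale limits | No |
| Exponentiated ratio and limits | No, and adding `CL` would not supply them |

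With period coded 1 and 2, the difference is migraine minus inter-ictal, the direction that SAP 7 uses.

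**3. Does the right interval follow from that output?** The interval is exp(difference ± t(0.95, df) × SE). Residual degrees of freedom are observations minus the rank of the period and patient effects.

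- 12 complete pairs: 24 − 13 = 11.
- 12 pairs plus 8 patients with Period 1 only: 32 − 21 = 11.
- 20 pairs: 40 − 21 = 19.

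With 11 df, t = 1.7959. Taking SE = 0.1112 and an estimated ratio of 1 as an illustration, the limits are exp(± 1.7959 × 0.1112) = exp(± 0.1997), or 0.819 to 1.221. This is the planned 90% interval, obtained without changing the model or the data.

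**4. How large would the feared error be?** Suppose `CL` were added to LSMEANS without `ALPHA=`.

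- 12 pairs: 2.2010/1.7959 = 1.226 times as wide on the log scale.
- 20 pairs: 2.0930/1.7291 = 1.210 times as wide.

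The upper half-width is exp(t × SD/√n) − 1. The SD of the within-patient log-ratio is an assumption, because the documents give only the inter-patient CV.

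| Pairs | Assumed SD | 90% | 95% |
|---|---|---|---|
| 12 | 0.20 | 10.9% | 13.6% |
| 12 | 0.385 | 22.1% | 27.7% |
| 12 | 0.545 (√2 × 0.3853) | 32.6% | 41.4% |
| 20 | 0.385 | 16.1% | 19.8% |

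The mistake would widen the intervals, not narrow them, and the same data would correct it. Nothing in either document plans that edit.

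**The case for a change.** The best case for a change is that the code exists to show how the stated output is obtained, and it stops short of that output. SAP 3 says that the SAP supersedes the protocol's statistical considerations and serves, with the TFL shells, as the template for the study report. Section 9.3.2 also ends with a leftover template placeholder, which suggests that it was not fully proofread. The TFL shells may state the level, but a 90% label on a shell would not correct a 95% calculation. The repair costs one line.

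The mismatch itself stands: as printed, the code outputs no interval, and the 0.1 on MODEL does nothing. The consequence does not stand. Adding `CL` would give log-scale limits only, so a processing step follows either way, and to say that none of the 18 intervals is output overstates an omission that this step fills. Nor is the placement of alpha an error in principle. Period has two levels, so under the default coding its coefficient is the Period 1 minus Period 2 difference, and asking MODEL for the solution with limits would return that contrast at 90%. What is missing is an output request, not an analysis decision. To report 95% limits as 90%, an analyst would have to overlook the sentence directly above the code.

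**Conclusion.** The observation about the code is correct, but it calls for no change. An analyst who follows the written plan reports the right 90% interval, because the text fixes everything that determines it and the printed output contains everything needed to compute it. The effect on every estimate, interval, population and decision is nil. The 1.226-fold widening arises only from an unplanned edit that would contradict the text, so it carries no weight. The statement in SAP 11 that nothing departs from the protocol is also not contradicted, since the example code alters no planned analysis.

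This rests on standard PROC MIXED option behaviour, which the documents do not describe; the code was not run in SAS. It also assumes that the analysts treat the block as the example it is labelled to be. The slip is clerical.

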9.4 Safety and Tolerability Assessments

9.4.1 Adverse events

Where changes in severity are recorded in the Case Report Form (CRF), each separate severity of the adverse event (AE) will be reported in the listings, only the most severe will be used in the summary tables. A pre-existing condition is defined as an AE that starts before the subject has provided written informed consent and is ongoing at consent. A non-treatment emergent AE is defined as an AE which starts after informed consent but prior to dosing. A treatment-emergent AE is defined as an AE which occurs postdose or which is present prior to dosing and becomes more severe postdose.

All AEs will be listed. Treatment-emergent AEs will be summarized by period, severity and relationship to the study drug. The frequency (the number of adverse events, the number of subjects experiencing an adverse event and the percentage of subjects experiencing an adverse event) of treatment-emergent adverse events will be summarized by period, Medical Dictionary for Regulatory Activities (MedDRA) version 20.0 system organ class and preferred term. The summary and frequency adverse event tables will be presented for all causalities and those considered related to the study drug. Any serious adverse events will be tabulated.

9.4.2 Concomitant medication

Concomitant medication will be coded using the World Health Organization (WHO) drug dictionary (Version March 2017 Enhanced Dictionary B2 Format). Concomitant medication will be listed.

9.4.3 Clinical laboratory parameters

All clinical chemistry, hematology and urinalysis data will be listed. Additionally clinical chemistry, hematology and urinalysis data outside the reference ranges will be listed.

Values for any clinical chemistry, hematology and urinalysis values outside the reference ranges will be flagged on the individual subject data listings.

9.4.4 Hepatic Monitoring

If a subject experiences elevated alanine aminotransferase (ALT) $\geq 3 \times$ upper limit of normal (ULN), alkaline phosphatase (ALP) $\geq 2 \times$ ULN, or elevated total bilirubin (TBL) $\geq 2 \times$ ULN, liver tests will be performed to confirm the abnormality.

The subjects' liver disease history and associated person liver disease history data will be listed. Any concomitant medication of acetaminophen/paracetamol will be listed. Results from any hepatic monitoring procedures, such as a magnetic resonance elastography (MRE) scan, and a biopsy assessment will be listed, if performed.

Hepatic risk factor assessment data will be listed. Liver related signs and symptoms data will be summarized by period and listed. Alcohol and recreational drug use data will also be listed.

All hepatic chemistry, hematology, coagulation, and serology data will be listed. Values outside the reference ranges will be flagged on the individual subject data listings.

9.4.5 Vital signs

Where supine blood pressure and pulse rate are measured in triplicate, the mean value will be calculated and used in all subsequent calculations. When triplicate blood pressure or pulse rate measurements precede a standing measurement, the last supine blood pressure or pulse rate measurement will be used for orthostatic calculations. Orthostatic will be calculated as the standing value, minus the last supine value taken prior to the standing value.

Vital signs data will be summarized by period together with changes from baseline, where baseline is defined as the mean of the triplicate measurement on Day 1 predose of each period for supine vital signs, and the last measurement on Day 1 predose of each period for standing and orthostatic vital signs. Figures of mean vital signs and mean changes from baseline profiles by period will be presented by period over time. Furthermore, values for individual subjects will be listed.

Changes from baseline will be calculated for vital signs. Changes from baseline of >30 mmHg for systolic blood pressure and of >20 mmHg for diastolic blood pressure are considered to be of potential clinical concern and will be highlighted on the individual changes from baseline data listings. Orthostatic decreases of >20 mmHg for systolic and diastolic blood pressure or an increase in heart rate of >20 bpm are considered to be of potential clinical concern, and will also be highlighted on the individual data listings.

9.4.6 Electrocardiogram (ECG)

For each subject, ECGs will be performed for safety purposes only, and will not be reported.

9.4.7 Columbia-Suicide Severity Rating Scale (C-SSRS)

Data from the C-SSRS questionnaire will be listed for individual subjects.

9.4.8 Other assessments

All other safety assessments not detailed in this section will be listed but not summarized or statistically analyzed.

9.4.9 Safety and Tolerability Statistical Methodology

No inferential statistical analyses are planned.

10. INTERIM ANALYSES

No interim statistical analyses are planned.

11. CHANGES FROM THE PROTOCOL SPECIFIED STATISTICAL ANALYSES

There were no changes from the protocol specified statistical analyses.

13. DATA PRESENTATION

13.1 Derived Parameters

Individual derived parameters (e.g. PK parameters) and appropriate summary statistics will be reported to three significant figures. Observed concentration data, e.g. C_{max} , should be reported as received. Observed time data, e.g. t_{max} , should be reported as received. N and percentage values should be reported as whole numbers. Median values should be treated as an observed parameter and reported to the same number of decimal places as minimum and maximum values.

13.2 Missing Data

Missing data will not be displayed in listings.

13.3 Insufficient Data for Presentation

Some of the TFLs may not have sufficient numbers of subjects or data for presentation. If this occurs, the blank TFL shell will be presented with a message printed in the centre of the table, such as, "No serious adverse events occurred for this study."

Leo Document ID = 62165d99-a18e-4969-93d3-6a6f112ece64

Approver: PPD

Approval Date & Time: 08-Aug-2017 07:18:59 GMT

Signature meaning: Approved

Approver: PPD

Approval Date & Time: 08-Aug-2017 07:53:30 GMT

Signature meaning: Approved

Approver: PPD

Approval Date & Time: 10-Aug-2017 15:21:14 GMT

Signature meaning: Approved

Approver: PPD

Approval Date & Time: 11-Aug-2017 13:18:03 GMT

Signature meaning: Approved
